4.4 Randomisation

Randomisation will take place on a site level (cluster). Each participating Talking Therapies site will be stratified and clustered according to demographics and then randomised using electronic randomisation software to either TherapyMatch-D (experimental) or AAU (control) condition. The aim of stratification is to control for sociodemographic characteristics as a potential confounding variable, and to identify a maximally diverse sample.

A site randomisation design has been adopted to minimise the chance of contamination which may occur if randomisation was applied at therapist or patient-level, since it is possible that a clinician who is familiar with the TherapyMatch-D model may apply this knowledge in AAU cases, or share this knowledge with other clinicians from the AAU group. This is particularly relevant in an Talking Therapies service because patients' clinical and demographic data are routinely available to all clinicians. Patients and clinicians will not be blinded to their allocation by virtue of the design.

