4.7 Primary and Secondary Outcomes and Measures

Primary outcome and measure

This study aims to pilot effectiveness of using a targeted prescription to guide treatment selection to improve clinical outcomes in depression relative to AAU, for which the main outcome variable is RCSI in depression. Effectiveness will be measured by the Patient Health Questionnaire-9 (PHQ-9) at the end of the treatment period (last session of CBT or PCE-CfD), with adjustment for baseline depression.

The PHQ-9 (Kroenke et al., 2001) is a brief measure commonly used to monitor the severity of depression and response to treatment. Each of the nine items is scored on a 0-3 scale. Item scores are summed to give an overall severity rating (range 0-27). The PHQ-9 has been validated for use in primary care (Kroenke et al.,2010), with adequate sensitivity (88%) and specificity (88%) estimates for the detection of major depressive disorder using a cut-off score ≥ 10 . RCSI was determined based on the method described by Jacobson and Truax (1991), by combining reliable change index (PHQ ≥ 6) and diagnostic cut-offs (PHQ-9 < 10).

Secondary outcomes and measures

The secondary outcome measures aimed to measure feasibility (adherence to the recommendation provided by the targeted prescription algorithm and outcome expectancy) and effects (anxiety, functional impairment, drop-out rates and adverse events). The specific variables were chosen as additional ways to measure improvement in clinical outcomes, to control for complexity and those variables that were identified to predict a differential response to treatment in the development of the targeted prescription

algorithm, and therefore needed to provide a targeted prescription recommendation of treatment (Delgadillo & Gonzalez Salas Duhne, 2020).

The specific measures for the secondary outcomes are:

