- Functional impairment. The Work and Social Adjustment Scale (WSAS; Mundt et al., 2002) questionnaire assesses the impact of mental health problems on 5 life domains (work, home management, social life, leisure activities, family and relationships) using Likert scales ranging from 0 (no impairment) to 8 (severe impairment). Scores across all 5 domains are summed to derive an overall score of functional impairment.
- Clinical and demographic variables. We will gather data relevant for the targeted prescription algorithm: age, employment status, self-reported disability, index of multiple deprivation, ethnicity, chronicity, and antidepressant medication. Additional data collected in routine primary mental healthcare and service utilisation data will include demographics, diagnoses, actual therapy offered, number of therapy sessions, types of treatments offered, reason for discharge, and last step accessed in stepped care system. Basic demographic data will also be collected from therapists (including age, gender, caseload, and qualifications) to explore potential differences in staff providing the intervention.
- Personality profile. This information will serve to control for variability in complex cases (Delgadillo et al., 2021) across sites. The Standardized Assessment of Personality–Abbreviated Scale (SAPAS) is an eight-item questionnaire developed to screen for the likely presence of a personality disorder (Moran et al., 2003). Each question prompts respondents to endorse specific personality traits (yes/no), yielding a total score between 0 and 8 where a cut-off >3 is indicative of cases with a high probability of diagnosable personality disorders.

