5.1. Sample size calculation

Pilot trials do not require a formal sample size calculation. However, a sample of at least 64 participants per arm is desirable (Teare et al., 2014) for a binary outcome in a pilot trial. We will aim to recruit 6-10 clusters (3-5 sites randomised in each arm) to allow subsequent sample size calculation for a definitive RCT. Within each Talking Therapies site, we will aim to recruit a minimum of 1 therapist that carry out routine assessment (maximum of 2 therapists per site). Each Talking Therapies site will aim to recruit 64 patients, For this, a total of 432 patients would be screened (216 patients per arm). As we expect approximately 30% of patients across sites to have a differential response, we estimate there would need to be 216 patients screened (64 patients per arm; 216*30% = 64). This calculation is based on the assumption of equal availability for treatment. As a pilot trial, any differences in treatment offer and waiting time for the different treatments will be reported and considered for potential subsequent research.

Overall, we will aim to recruit a minimum of 6-10 therapists that carry out routine assessments across the 6-10 Talking Therapies services (1 to 2 per Talking Therapies service). Between the 6 to 20 therapists, we expect that they will assess at least 432 during a 1-year study period, which would require each therapist to assess 1 to 2 cases per week on average.

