5.2. Primary analysis

Patient-level clinical outcome data will be analysed using logistic multilevel modelling conducted according to the intention-to-treat principle according to CONSORT guidelines for Cluster RCTs. Researchers will be blinded to the group allocation while analysing the trial data.

The primary outcome will be defined as reliable and clinically significant improvement (RCSI) in depression symptoms (PHQ-9) after treatment, based on the method described by Jacobson and Truax (1991). A 3-level model will be applied, with patients nested within therapists, nested within Talking Therapies sites, and post-treatment RCSI in depression (PHQ-9) symptoms as the dependent variable. Group (TherapyMatch-D vs. usual care) will be entered as a level-2 predictor, along with baseline PHQ-9 as a level-one covariate. This method will enable us to determine whether TherapyMatch-D is associated with a greater treatment effect (depression symptom reduction) by comparison to usual care and will be specifically run in the target sample of patients identified as having a differential response to treatment. The three-level model will account for the nested structure of the data, as appropriate within a cluster trial design. Given the small sample sizes of this pilot trial, it is unlikely the estimates of random effects for site and therapist will be reliable, but this data may be used to guide subsequent research. If the site and therapist random intercepts are not statistically significant, a one-level parsimonious multivariate regression model will be estimated as a sensitivity analysis. Adjusted odds ratios and confidence intervals will be reported as a primary effect sizes. In addition, we will also report the results in the best fitting model following analyses of goodness of fit to find the most parsimonious model.

We acknowledge that some patients might decide to switch from one therapy to another following allocation in either arm of the trial (i.e., patient allocated to CBT after consenting to treatment asks to switch to PCE-CfD), as occurs in routine practice occasionally. In this pilot trial, we will report the frequency of this occurrence and circumstances. Cases will be included in the primary analysis (as part of the

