4.3. Secondary analyses

The above modelling strategy will be repeated to compare the rate of improvement (RCSI) in GAD-7 anxiety symptoms, and RCSI in depression symptoms only in the cases who attended at least one treatment session. We will also compare outcome expectancy, dropout rates and adverse effects between groups, and compare characteristics between those who attended at least one treatment session versus those who dropped out following assessment. For both TherapyMatch-D and control groups, we will estimate the proportions of participants who had RCSI post-treatment, and who completed/dropped out of treatment. We will also calculate and report effect sizes for each of the symptom measures (PHQ-9, GAD-7, WSAS) using Cohen's *d* metric (Cohen, 1988), based on mean differences between groups. Treatment attendance, completion, and dropout rates will be presented diagrammatically and based on CONSORT guidelines. To quantify any potential adverse effects related to the trial, we will also calculate a rate of reliable deterioration in patients across both arms of the trial. Further, we will use the data collected to identify complex cases (see StratCare Trial from Delgadillo et al., 2021) and control for variability in complex cases across Talking Therapies sites.

We will examine adherence to the TherapyMatch-D model using the full study sample of participants with a differential treatment response across both arms. Each therapist's Treatment-Matching Precision Score (TMaP) will be calculated, which is a statistical measure of agreement between their observed treatment selection and the recommendations made using the prognostic algorithm. In the experimental group, this would represent the agreement of patients accepting the recommended treatment. In the control group, this is the post-hoc analysis of the agreement the optimal treatment that the prescriptive algorithm would recommend (which patients did not receive, since they were in the control group) and the actual treatment selected via shared decision making. A comparison of mean TMaP scores between groups will be done using parametric or non-parametric tests, depending on the distribution of TMaP scores.

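### The primary model adjusts for baseline PHQ-9 but not for the case complexity that the protocol measures in order to control for it, and only 3-5 sites per arm are randomised

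*Protocol*

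**What the plan says.** Protocol section 4.7 gives, among the reasons for choosing the measures, "to control for complexity and those variables that were identified to predict a differential response to treatment". Of the personality profile (SAPAS, scored 0 to 8) it says: "This information will serve to control for variability in complex cases" across sites. Section 4.8 has SAPAS completed at assessment in both groups.

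Section 5.2 then fixes the covariates of the three-level logistic model for RCSI: group enters at level 2, "along with baseline PHQ-9 as a level-one covariate". No other covariate is named.

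Complexity returns in the Secondary analyses subsection of section 5 (numbered 4.3), where the data will be used to identify complex cases and "control for variability in complex cases across Talking Therapies sites". That sentence names no outcome, no model and no form of the covariate.

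On design, section 4.4 randomises sites and explains that "The aim of stratification is to control for sociodemographic characteristics as a potential confounding variable". Section 5.1 states: "We will aim to recruit 6-10 clusters (3-5 sites randomised in each arm". Section 5.2 itself doubts that the site and therapist random effects will be reliably estimated.

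**The concern.** The protocol identifies a patient characteristic that it expects to vary between sites, and it measures that characteristic at baseline in both arms for the purpose of control. It then leaves it out of the analysis that carries the primary effect size.

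Few-cluster randomisation makes this matter more than it would in an individually randomised trial:

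- Three to five sites per arm cannot be relied on to balance clinical case-mix, and complexity is not a stratification factor.
- One or two therapists per site obtain consent after the site has been allocated. Section 4.4 says that clinicians are not blinded, and section 4.5 expects therapists to deduce their allocation. Differences in who is recruited could add to chance imbalance.
- A well-estimated site intercept would carry such imbalance into the confidence interval. Section 5.2 doubts that estimate, and its one-level sensitivity model drops the intercept.

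What is at stake is how far the pilot's adjusted odds ratio can be trusted when a definitive trial is planned. If complexity is left to an unattached secondary sentence, the decision to adjust may also be taken after the imbalance has been seen.

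**Working it through.** **1. The plan's own figure.** Section 5.1 gives 64 differential responders per arm: 216 × 0.30 = 64.8, and 432 × 0.30 = 129.6 against the stated 128. Both reproduce within two patients. Per site this is 128/6 = 21.3 or 128/10 = 12.8 analysed patients.

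**2. Inputs.** From the protocol: 3 or 5 sites per arm (k), about 21 or 13 patients per site (n), and recovery of about 50% (section 2). Assumed, because the protocol gives no value: mean share of complex cases p = 0.30; between-site SD of that share s = 0.05 to 0.15; odds ratio of complexity for RCSI, net of baseline PHQ-9, 0.4 (strong) or 0.6 (mild).

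**3. Between-arm difference d in the share of complex cases.**

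SD(d) = √{(2/k) × [s² + (p(1−p) − s²)/n]}

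- k = 3, n = 21, s = 0.15: √{(2/3) × [0.0225 + 0.1875/21]} = 0.145
- k = 5, n = 13, s = 0.05: √{(2/5) × [0.0025 + 0.2075/13]} = 0.086
- Reference, individual randomisation of 64 per arm: √(2 × 0.21/64) = 0.081

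Simulation (20,000 draws per scenario) agrees: SD 9-15 points with 3 sites per arm and 9-12 with 5. The chance of a difference above 10 points is 25-48% and 24-42% respectively.

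**4. Effect on the odds ratio when there is no true effect.** With overall RCSI at 50%, log OR shift ≈ d × (RCSI rate in non-complex − RCSI rate in complex) / (0.5 × 0.5).

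- Odds ratio 0.4: rates 56.7% and 34.4%, so 0.223/0.25 = 0.89 per unit of d. The 95% limit with SD(d) = 0.145 is exp(1.96 × 0.145 × 0.89) = 1.29. Simulated range: 0.77-1.29.
- Odds ratio 0.6: rates 53.8% and 41.1%, so 0.127/0.25 = 0.51 per unit of d. The 95% limit with SD(d) = 0.086 is exp(1.96 × 0.086 × 0.51) = 1.09. Simulated range: 0.92-1.09.

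**5. Scale against sampling error.** Take 64 per arm and RCSI of 50% v 70% (odds ratio 2.33, the retrospective study quoted in section 2). Then SE(log OR) = √(1/32 + 1/32 + 1/44.8 + 1/19.2) = 0.370, and the 95% factor is exp(1.96 × 0.370) = 2.06 each way. With an assumed ICC of 0.05 the design effect is 1 + 20.3 × 0.05 = 2.02 (3 sites per arm) or 1 + 11.8 × 0.05 = 1.59 (5 sites per arm), giving factors of 2.80 and 2.50. The complexity component is well inside this.

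**6. Precision gained by adjusting.** This was simulated with 128 patients, 6 or 10 sites, 30% complex, a site SD of 12 points, a binary complexity indicator, single-level logistic models and 3,000 trials per setting. The measure is (mean log OR / SD of log OR)², compared with and without the indicator.

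- Complex cases end 2 PHQ-9 points worse: change between −0.3% and +1.6%.
- Complex cases end 4 points worse: gain 8-13%.
- Complexity adds nothing beyond PHQ-9: loss of 1-2%.

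Without the indicator, the estimated log OR correlates with the imbalance at about −0.16 to −0.20 (2 points) or −0.32 to −0.36 (4 points). With it, the correlation is within 0.04 of zero.

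**The case against.** The strongest reply is that nothing is contradicted. Sections 4.7 and 5 say that complexity will be controlled, not that it will be controlled in the primary model. A small primary model with a case-mix-adjusted secondary analysis is a legitimate design. This stands: the point is a weak choice in section 5.2, not an inconsistency.

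A reader might also infer more than the protocol supports:

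- *That the headline result is unadjusted.* It is adjusted for baseline PHQ-9, and sites are stratified on sociodemographic characteristics. The gap is clinical complexity only.
- *That no rule says which estimate counts.* The primary and secondary headings supply that rule.
- *That the odds ratio is biased.* Chance imbalance between randomised sites is random error. Selective recruitment after randomisation could bias it, but the protocol offers no evidence that it will occur, and adjustment would remove only the part captured by the score.
- *That adjustment buys substantial precision.* It does so only if complexity is strongly prognostic net of PHQ-9. Four points against an assumed residual SD of 5.3 is 0.75 SD. The SD of the log OR rises slightly on adjustment, and any gain comes from a larger conditional odds ratio.

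Section 2 links complexity to poorer response but gives no effect net of baseline PHQ-9, so prognostic strength remains an assumption. Which secondary model the complexity sentence belongs to may fairly be left to a statistical analysis plan. The primary covariates are different, because section 5.2 has already fixed them. It is also fair that the pilot tests no hypothesis (section 3.3). Its odds ratio is nonetheless declared the primary effect size.

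**Conclusion.** The concern holds at modest severity. The protocol measures complexity at baseline in both arms in order to control for it, and then omits it from the primary model, in a design with few clusters that does not balance it otherwise.

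Under the assumed inputs, chance imbalance could move the primary odds ratio within 0.92-1.09 at the mild end and 0.77-1.29 at the strong end. This is one removable part of the random error, and it is smaller than the sampling factor of about 2.1 to 2.8 each way. The case for change rests mainly on removing the estimate's dependence on a known imbalance, and on settling the choice before the data are seen. It does not rest on precision. The prevalence, the between-site spread and the prognostic strength are all assumptions. The calculations used a binary indicator, so the yield from the SAPAS total could differ.

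**What to change.** In section 5.2, state the primary model as group, baseline PHQ-9 and the baseline SAPAS total score, the last two at patient level. Naming SAPAS matters because the complexity classification under Secondary analyses is defined only by reference to another trial. Use the same covariates when the model is repeated for the secondary outcomes, and say which outcome and model the complexity sentence there refers to. Report the primary model without SAPAS as a sensitivity analysis. Its odds ratio may differ a little even under perfect balance, because a logistic odds ratio changes when a prognostic covariate is added.

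The cost is one parameter. At about 50% recovery, 128 patients give some 64 events for three fixed effects, or about 21 each. If SAPAS adds nothing beyond PHQ-9, the loss is about 1-2%. A simple rule is needed for missing baseline SAPAS scores, such as a baseline imputation or a missing indicator. No new data are collected, since SAPAS is already scheduled at assessment in both groups.

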Primary outcome(s)	Reliable and Clinically Significant Improvement in depression using a	
	patient-level measure (PHQ-9).	
Randomisation and	Consenting Talking Therapies sites will be randomly assigned to an	
interventions	intervention group labelled 'TherapyMatch-D' or a control group labelled	
	'allocation as usual' (AAU). Consenting therapists of sites in both groups will be trained to use a computer programme called TherapyMatch-D	
	containing an algorithm which will identify consenting patients with a	
	differential treatment response (prior research suggests would be approx.	
	30% of the sample). From that sub-sample, patients in TherapyMatch-D	
	group will be provided a personalised treatment selection recommendation	
	(between CBT and PCE-CfD) based on the targeted prescription algorithm to	
	be used alongside shared decision making. Patients in AAU group will be	
	allocated to treatment as usual (treatment selection based solely on	
	shared-decision making). All patients without an identified differential	
	treatment response across both groups (estimated to be approx. 70%) will	
	also be allocated as usual to treatment (i.e., either CBT or PCE-CfD).	
Planned Sample Size	Pilot trials do not require a formal sample size calculation. However, we will	
	aim to recruit 6-10 clusters (3-5 sites randomised in each arm) with a total of	
	432 patients screened (216 patients per arm). As we expect approximately	
	30% of patients to have a differential response, we estimate there would be	
Data analysis mesthes	128 eligible patients (64 patients per arm).	
Data analysis method	1. Trial data will be summarised using a CONSORT diagram and	
	analyses will be based on intention-to-treat principles.Patient-outcome data will be analysed using multi-level logistic	
	regression. Post-treatment reliable and clinically significant improvement	
	Tregression. Fost-treatment reliable and chincally significant improvement	

	(RCSI) in depression symptoms will be the primary outcome, and will be compared between TherapyMatch-D and AAU. 3. The primary aim will be to examine between-group differences comparing cases using the treatment selection model versus AAU, in the sample of patients where a differential treatment response was identified. 4. Secondary analyses will involve comparing between-group differences in anxiety symptoms, functional impairment, dropout rates, and
	outcome expectancy, and adverse events.

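### Section 5.2 lets non-significant site and therapist intercepts, and a parsimony search, bring in an unclustered model, and does not say which model gives the primary odds ratio

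*Protocol*

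**What the plan says.** Section 4.4 randomises whole sites. Section 5.2 specifies a 3-level logistic model (patients within therapists within sites) and justifies it by the cluster design. It then qualifies this in three steps.

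- On the variance components it concedes that "it is unlikely the estimates of random effects for site and therapist will be reliable".
- It makes a second model depend on testing those components: "If the site and therapist random intercepts are not statistically significant, a one-level parsimonious multivariate regression model will be estimated as a sensitivity analysis".
- After stating that adjusted odds ratios with confidence intervals are the primary effect sizes, it adds that "we will also report the results in the best fitting model following analyses of goodness of fit to find the most parsimonious model".

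The section on secondary analyses (numbered 4.3, but placed after 5.2) opens with "The above modelling strategy will be repeated", so the same steps apply to anxiety RCSI and to depression RCSI among patients who attended at least one session.

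Section 5.1 gives the scale: "We will aim to recruit 6-10 clusters (3-5 sites randomised in each arm) to allow subsequent sample size calculation for a definitive RCT", with a "minimum of 1 therapist that carry out routine assessment (maximum of 2 therapists per site"). The synopsis expects "128 eligible patients (64 patients per arm") in the primary analysis. Section 3.3 says that, as a pilot, the study tests no hypotheses.

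**The concern.** In a cluster trial the site term reflects how treatment was assigned, so it belongs in every arm comparison whatever its estimate or p-value. Section 5.2 makes an unclustered analysis depend on a test of variance components that it has just called unreliable. A non-significant result from so few sites is what one expects whether or not outcomes differ between sites.

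The search for a parsimonious best-fitting model leads the same way. It carries no sensitivity label, and a fit criterion with little power to detect site variance will usually drop it. Because the source of the primary effect size is not named, up to three odds ratios with different intervals could be reported, and the reader would not know which is primary. At stake is the honesty of the intervals for the primary outcome and for the secondary outcomes that reuse the strategy, in a pilot meant to inform a definitive trial.

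**Working it through.** **The plan's own figure.** Section 5.1 gives "64 patients per arm; 216*30% = 64". 216 x 0.30 = 64.8 per arm and 432 x 0.30 = 129.6 in total, so the stated 64 and 128 are reproduced up to rounding down.

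**Inputs.** From the protocol: 128 analysed patients and 6 to 10 sites. Assumed, because the protocol gives none: ICC 0.01 to 0.10, RCSI rate 40% to 50% (section 2 cites recovery of about 50%), and 95% intervals.

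**Formulas.**
- Mean site size m = 128/k: 128/6 = 21.3 and 128/10 = 12.8.
- Design effect DEFF = 1 + (m - 1) x ICC. At ICC 0.05: 1 + 20.33 x 0.05 = 2.02 (6 sites) and 1 + 11.8 x 0.05 = 1.59 (10 sites).
- One-level standard error relative to the true one: 1/sqrt(DEFF), that is 0.70 and 0.79.
- Coverage of the one-level interval: 1 - 2 x [1 - Phi(1.96/sqrt(DEFF))]. At ICC 0.05, 1.96/1.42 = 1.38 gives 83.2%, and 1.96/1.26 = 1.55 gives 88.0%.

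| ICC | Sites | DEFF | SE ratio | Coverage, formula | Coverage, simulated (log-odds-scale ICC) | Site intercept non-significant |
|---|---|---|---|---|---|---|
| 0.01 | 6 | 1.20 | 0.91 | 92.6% | 93-94% | 98% |
| 0.01 | 10 | 1.12 | 0.95 | 93.6% | 94% | 97% |
| 0.05 | 6 | 2.02 | 0.70 | 83.2% | 86% | 88% |
| 0.05 | 10 | 1.59 | 0.79 | 88.0% | 90% | 88% |
| 0.10 | 6 | 3.03 | 0.57 | 74.0% | 78% | 71% |
| 0.10 | 10 | 2.18 | 0.68 | 81.6% | 85% | 68% |

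The simulated coverage is 100% minus the rejection rate of the one-level model in 100,000 null trials per setting, at RCSI 40% and 50%. With the ICC on the observed-proportion scale, the simulation agrees with the formula: at RCSI 40% and ICC 0.05 the rejection rates are 17.1% and 12.0%, so coverage is 82.9% and 88.0%. The last column comes from 4,000 null trials per setting at RCSI 45%, using a one-sided 5% likelihood ratio test of a random site intercept with the ICC on the log-odds scale. An ICC of the same size on the observed scale is stronger clustering, and the test then fires somewhat more often.

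**Does the pre-test protect?** No. With 6 sites and ICC 0.05, the one-level interval misses the true value in 14.9% of the trials where the intercept is non-significant, against 14.6% of all trials.

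**Is keeping the site term enough?** Not with a Wald z interval. With 6 sites, the random-intercept model misses in 11% of trials at ICC 0.05 and 14% at 0.10. With 10 sites the figures are about 6.5% and 8%. One reason is that the site variance is often estimated as exactly zero: in 47% of trials (6 sites) and 41% (10 sites) at ICC 0.05. A t-test on site-level summaries with k - 2 degrees of freedom errs in 4.8% to 6.0% across 6 and 10 sites and ICC 0.01 to 0.10.

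**Limits.** Site sizes were near equal, baseline PHQ-9 was left out, and site and therapist were one variance. The last is close to the plan where a site has a single therapist, because the two levels then coincide.

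**The case against.** The strongest defence is that the primary analysis is already clustered. The one-level model is labelled a sensitivity analysis, the best-fitting model is an addition, and the text warns openly that the random effects are weakly estimated. All of that stands. A reader might infer that the trial falls back to an unclustered primary result. The protocol does not say so; what it leaves open is which model supplies the primary effect size.

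A reader might also put the harm as a false-positive rate of 10% to 20%. Two things count against that. Section 3.3 rules out hypothesis testing, so interval coverage is the better measure. And the figure depends on an ICC that the protocol never gives: by formula the one-level error is about 6-7% at ICC 0.01 and up to 26% at ICC 0.10 with 6 sites.

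Two further inferences go too far. One is that the one-level result will look more precise than the clustered one in almost every run. When the site variance is estimated as zero, which is common here, the two coincide. The other is that the one-level odds ratio would be used to size the definitive trial. Section 5.1 ties the number of clusters to that calculation, and section 5.2 says the random-effect estimates may guide later research, but neither mentions the one-level result.

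The sensitivity label does not dispose of the point. A sensitivity analysis should probe an assumption that could plausibly hold. This one assumes independence within the randomised unit, on evidence that cannot support it, and the best-fitting model does not carry the label at all.

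**Conclusion.** The point holds as a defect in how section 5.2 chooses and reports models, and it extends to the secondary analyses that reuse the strategy. It does not mean that the stated primary model is unclustered. The trigger will be met in most trials of this size: about 97-98% at ICC 0.01, 87-88% at 0.05 and 68-71% at 0.10. The one-level interval it produces covers about 93-94%, 83-88% and 74-82% respectively, where 95% is claimed. If the true ICC is near 0.01 the loss is small; at 0.05 the interval is 21% to 30% too narrow (1 - 0.79 and 1 - 0.70). All these figures rest on assumed ICCs and on the simplifications listed above. That a non-significant intercept says little about clustering with 6 to 10 sites holds across the whole range. Only the protocol was at hand; a separate analysis plan might name the primary model, but the protocol text would still need correcting.

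**What to change.** In section 5.2, and by reference in the secondary analyses:

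1. Name the clustered model as the only source of the primary odds ratio and confidence interval.
2. State that site clustering stays in every arm comparison, whatever its estimate, p-value or fit statistic.
3. Remove the significance trigger and the fit-based choice of random effects. If a one-level result is still wanted, report it as unadjusted for clustering and not for inference.
4. Use a small-sample method throughout, not only when the model fails to converge or returns zero variance: for example a site-level summary analysis on sites minus 2 degrees of freedom, or a degrees-of-freedom correction to the mixed model.

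The cost is a few sentences, a little more analysis work and no extra data. Intervals will be wider. In the site-level analysis the multiplier rises from 1.96 to the t quantile, 2.78 on 6 - 2 = 4 degrees of freedom or 2.31 on 10 - 2 = 8. That width reflects what 6 to 10 randomised sites can show.
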